In addition to its test characteristics, the binx *io* has additional properties, such as ease of use and rapid specimen processing time, that may be advantageous over the point-of-care gram stain and could ultimately inform CDC recommendations for point-of-care diagnostics in specialized sexual health clinic settings. Furthermore, understanding the implementation process of the binx *io* in specialized STI care settings could inform wider uptake of similar rapid molecular diagnostic tests in other clinical settings where STIs are managed.

2. Specific Aims and Objectives

Aim 1. To evaluate the impact of the binx *io* platform, compared to point-of-care gram stain, on antibiotic use in the clinical management of patients with symptomatic urethritis and cervicitis presenting to the Massachusetts General Hospital Sexual Health Clinic (SHC). We will conduct a randomized controlled pilot trial comparing the mean number of antibiotic courses administered per patient when evaluated with either point of care gram stain (current standard of care in MGH SHC) or the binx *io* platform. Secondary outcomes include concordance of binx *io* and point-of-care gram stain results for gonorrhea, concordance of binx *io* and nucleic acid amplification test (NAAT) results for gonorrhea and chlamydia, and time to provision of

Expedited Partner Therapy (EPT) for eligible patients with chlamydia. Hypothesis: Clinical management based on the results of the binx *io* will decrease the mean number of antibiotic courses administered per patient by 10%.

Aim 2. To evaluate the implementation of the binx *io* platform in a specialized sexual health clinic using mixed methods. Quantitative analysis will assess process measures including rate of invalid results, equipment errors, processing time, and patient visit duration. We will conduct a focus group discussion with MGH SHC staff to assess impressions of use of the testing platform and other potential uses of point-of-care testing in the STI management pathway.

3. General Description of Study Design

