Per standard clinic procedures, participants will be contacted by phone with results of NAAT gonorrhea and chlamydia testing from MA DPH if these results require additional treatment that was not provided during the initial clinic visit. Participant contact and treatment will be provided according to standard clinical procedures of the Sexual Health Clinic. After one week following the visit, the study team will review the participant's chart to record DPH test results and any resulting additional treatment. 30 days following the initial visit, the study team will record additional antibiotics prescribed for participants with unresolved symptoms.

In addition to specimens collected for immediate clinical use, all participants in both the intervention and control groups will be asked to provide an additional vaginal or urethral swab for storage. These specimens may be used in future studies of STI diagnostics. Any extra unused urine specimens may also be stored for use in future studies of STI diagnostic tests. Participants will be asked to consent to the collection and use of these additional vaginal, urethral, or urine specimens for future research. These specimens may be cultured in an incubator prior to storage in a freezer in the laboratory space on Jackson 7. Stored specimen will be labelled with a unique identification number. Following the conclusion of this study, each new use of these samples will be submitted in a secondary use protocol for MGB IRB approval. Specimen collection is summarized in the table below.

Table 1: Specimen Collection

Control Arm	Intervention Arm
-------------	------------------

Consented to research specimen collection?	No	Yes	No	Yes
Male	1) 1 or 2 urethral swabs	1) 1 or 2 urethral swabs 2) Urine sample	1) 1 or 2 urethral swabs 2) Urine sample	1) 1 or 2 urethral swabs 2) Urine sample
Female	1) 2 cervical swabs	1) 2 cervical swabs 2) One vaginal swab	1) 2 cervical swabs 2) 1 vaginal swab	1) 2 cervical swabs 2) 2 vaginal swabs

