Participants in the focus group discussion may benefit by improving understanding of effective ways to incorporate rapid testing into specialized STI care, thus potentially improving their work experience and ability to care for patients in the future.

9. Statistical Analysis

Sample size calculation

We hypothesize that the use of the binx *io* platform will decrease the mean number of antibiotic courses per patient by 10%. Based on data from 2020, symptomatic patients would receive approximately 1.13 courses of antibiotics per patient. With an alpha of 0.05, we would have a power >90% to detect a decrease of 10% (to 1.017 per patient) with sample size of 100 (50 per arm).

Analysis plan

The primary outcomes for Aim 1 will be compared between patients randomized to clinical management based on the binx *io* and patients randomized to clinical management based on point-of-care gram stain. Demographic and clinical data for both cohorts will be obtained from the SHC RedCap database and supplemented with chart review as necessary.

Standard descriptive statistics will be used to report primary and secondary clinical outcomes, reported as proportions, means with standard deviation, or median with interquartile range as appropriate. Unadjusted and adjusted ordinal logistic regression models will be used to compare the total antibiotics administered between patients for whom the binx *io* vs point of care gram stain was used for clinical management. Adjusted models will incorporate predictors felt clinically to affect likelihood of antibiotic administration as well as those found to be significant in unadjusted analyses, including gender, age, race/ethnicity, and insurance status.

Transcripts from the focus group discussion will be transcribed, coded, and analyzed for key themes deductively and inductively using content analysis.

10. Monitoring and Quality Assurance

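### The hypothesis is a 10% fall in mean antibiotic courses, but the only between-arm analysis named is an ordinal model, and no difference or ratio of means with a CI is pre-specified

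*Combined protocol and SAP*

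**What the plan says.** - **Aim 1 (section 2)** describes a pilot randomised trial "comparing the mean number of antibiotic courses administered per patient when evaluated with either point of care gram stain" or the binx io. The hypothesis there is a 10% fall in that mean.
- **Sample size calculation (section 9)** repeats the hypothesis. It takes the control value from 2020 data ("symptomatic patients would receive approximately 1.13 courses of antibiotics per patient") and claims power above 90% for a fall to 1.017 with 50 per arm. It gives no SD, distribution, test or sidedness.
- **Analysis plan (section 9)** says that the Aim 1 primary outcomes will be compared between arms, without naming a method in that sentence. Outcomes are to be "reported as proportions, means with standard deviation, or median with interquartile range as appropriate". The one between-arm method named is: "Unadjusted and adjusted ordinal logistic regression models will be used to compare the total antibiotics administered between patients".
- **Section 6** has the team review charts after one week to "record DPH test results and any resulting additional treatment", and at 30 days record further antibiotics for unresolved symptoms. The plan does not say whether these count in the total.

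No difference in means, ratio of means, confidence interval or model-predicted mean by arm appears anywhere.

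**The concern.** The question is asked on one scale and answered on another. A proportional-odds model estimates how the odds of receiving more courses differ between arms. The shift in the mean implied by that odds ratio depends on how control patients are spread over 0, 1, 2 or more courses. A reader given only the planned odds ratio could learn the direction of effect, but not whether the mean fell by about 10%.

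The 10% hypothesis therefore has no pre-specified estimate with an interval. A larger trial with the same hypothesis would also need the mean difference and its precision from this pilot. If the scale is left open, someone will have to choose it after seeing the results.

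**Working it through.** **Inputs.** From section 9: control mean 1.13, target mean 1.13 × 0.9 = 1.017, difference 0.113, 50 per arm, alpha 0.05. The documents give no distribution of courses, so every split below is an assumption, chosen to have mean 1.13.

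**The plan's own figure.** For a two-sided comparison of two means, 90% power needs SD ≤ 0.113 / [(1.960 + 1.282) × √(2/50)] = 0.174. The lowest pooled SD that whole-number counts with these means can have is √[(0.13 × 0.87 + 0.017 × 0.983)/2] = 0.255, which gives 60% power. The stated figure of over 90% is not reproduced this way, and with no SD or test given its source cannot be identified. That is a separate matter. It is relevant here only because the power statement does not show which analysis it belongs to.

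**Step 1: same fall, different odds ratio.** Under proportional odds, the odds of k or fewer courses in the binx arm equal the control odds divided by OR. I solved for the OR that brings the mean to 1.017.

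Worked example, control .10/.67/.23 for 0/1/2 courses, OR 0.651:
- Odds of 0 courses: (0.10/0.90)/0.651 = 0.171, so probability 0.146.
- Odds of 0 or 1: (0.77/0.23)/0.651 = 5.143, so probability 0.837.
- Mean: (1 − 0.146) + (1 − 0.837) = 1.017.

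**Step 2: same odds ratio, different fall.** I applied OR 0.65 to the same splits. For .02/.83/.15 the odds of 0 courses become 0.0204/0.65 = 0.0314 (probability 0.030), and the odds of 0 or 1 become 5.667/0.65 = 8.718 (probability 0.897). The mean is 0.970 + 0.103 = 1.072, a fall of 5.1%.

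| Assumed control split (0/1/2 or 0/1/2/3) | OR giving a 10% fall | Fall in mean at OR 0.65 |
|---|---|---|
| .02/.83/.15 | 0.40 | 5.1% |
| .05/.77/.18 | 0.54 | 7.1% |
| .10/.67/.23 | 0.65 | 10.0% |
| .25/.37/.38 | 0.77 | 16.3% |
| .30/.37/.23/.10 | 0.80 | 19.2% |

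Proportional odds holds exactly in every row, so the spread does not come from model misfit.

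**Step 3: when proportional odds does not hold.** Four assumed pairs, all with means 1.13 and 1.017, were fitted by maximum likelihood. Power is from 40,000 simulated trials at 50 per arm, comparing the Welch test with the tie-corrected Wilcoxon test (the score test of the ordinal model).

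| Control → binx | Fitted OR | Power, Welch | Power, ordinal score |
|---|---|---|---|
| .10/.67/.23 → .05/.883/.067 | 0.53 | 23.0% | 25.7% |
| .10/.67/.23 → .16/.663/.177 | 0.66 | 16.4% | 16.1% |
| .25/.37/.38 → .15/.683/.167 | 0.70 | 12.8% | 15.8% |
| .25/.42/.28/.05 → .25/.483/.267/0 | 0.81 | 10.8% | 8.8% |

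Welch is 3.0 points lower to 2.0 points higher. Where proportional odds holds, the two agree to within about 0.2 points.

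**Step 4: what the mean-scale interval would look like.** Half-width is about 1.984 × √[(s₁² + s₂²)/50].
- Narrowest split (SDs 0.391 and 0.338): 1.984 × √(0.2672/50) = 0.145.
- Widest split (SDs 0.956 and 0.936): 1.984 × √(1.790/50) = 0.375.

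Simulated coverage of the 95% interval is 94.7% to 95.2%.

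**The case against.** The strongest reply is that the mean is not absent. Aim 1 promises a comparison of means, section 9 says the primary outcomes will be compared, and means with SDs are among the listed summaries. With mean, SD and n per arm, any reader can form a difference and a Welch interval. The control distribution will also be observed, so nobody would have to interpret the odds ratio without it. An ordinal model is a defensible choice for a short count, the two tests have similar power, and this is a pilot of 100 patients.

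Much of this stands. The ordinal test is a valid test of no difference under proportional odds and agrees in direction with the mean. The 5.1% to 19.2% range shows what the odds ratio alone leaves open before data; it does not show that a full report would hide the change. It is also fair that a half-width of 0.145 to 0.375, against a target of 0.113, means the proposed interval will generally not settle whether the fall is 10%.

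None of it supplies the missing step. The plan leaves open whether means, medians or proportions are reported. It specifies no interval, and it does not say that a crude difference is the analysis of the hypothesis. The wide interval is itself something readers should see on the scale of the hypothesis.

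**Conclusion.** The concern holds. Aim, hypothesis and power statement are on the mean scale; the only named between-arm analysis is not, and nothing links the two. Under the assumed splits, the hypothesised 10% fall could appear as an odds ratio anywhere from 0.40 to 0.80, even with the ordinal model exactly right.

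The consequence is a missing estimate, not an invalid test. Whether proportional odds is plausible cannot be judged from the documents: they give no course distribution and do not say whether later treatment counts. The reading of the plan does not depend on the assumed splits; the sizes do. This should be changed, and the change is cheap.

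**What to change.** Name, as the analysis that addresses the hypothesis, the difference in mean courses (binx io minus gram stain) with a 95% CI, and report the ratio of means with its 95% CI alongside. Use linear regression for the difference and a log-link model for the ratio, both with robust standard errors. Model-based Poisson errors would be too wide under these splits: the Poisson SD is √1.13 = 1.06, against control SDs of 0.39 to 0.96. Keep the ordinal model as supportive, and tabulate the distribution of courses by arm. State whether treatment recorded at the later chart reviews counts in the total.

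If the team prefers the ordinal model as primary, a coherent alternative is to restate the hypothesis and power as an odds ratio with an assumed course distribution, and to report model-predicted mean courses by arm and their difference with a bootstrap 95% CI.

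The cost is SAP wording and a few lines of code, with no new data. The downside is a little more analysis work and the power difference shown in step 3.

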This study is a pilot randomized controlled trial evaluating the use of either a) the binx *io* or b) point-of-care gram stain (current standard of care) to guide clinical management of patients with symptomatic urethritis or cervicitis evaluated in the MGH Sexual Health Clinic. Patients presenting with symptoms of urethritis or cervicitis and meeting inclusion criteria will be randomized to have diagnostic specimens tested during the clinical encounter using either the binx *io* platform or point-of-care gram stain. Patients randomized to the intervention arm of the study will also have a gram stain slide created, which will be held for later interpretation following the clinical encounter. Participants will not be followed longitudinally. Towards the end of the study, we will conduct a focus group discussion with Sexual Health Clinic staff to explore their impressions of use of a rapid STI test in the clinic and other potential uses of rapid STI testing in STI clinical management.

A detailed study schema is attached.

4. Subject Selection

The study will take place in the Massachusetts General Hospital Sexual Health Clinic (SHC), a specialized sexually transmitted infection (STI) clinic operated in partnership with the Massachusetts Department of Public Health. The clinic is staffed by nurse practitioners and physicians, who see patients for scheduled and urgent care visits.

Potential participants will be identified for recruitment by the Sexual Health Clinic staff upon review of the reasons given for scheduled or urgent care appointments for the day. Additionally, any patient who reports symptoms of urethritis or cervicitis during the clinic encounter, regardless of the reported chief complaint for the visit, will be assessed for eligibility by the clinician. Participants will be approached by a research assistant to introduce the study and obtain informed consent. Consenting participants will be

randomized to either the intervention or control group using a randomization function in RedCap.

Patients presenting to the Sexual Health Clinic will be eligible to participate in the study based on the following criteria:

Inclusion criteria

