6. STUDY PROCEDURES

All study procedures will take place during the patient's index clinic visit. All participants will undergo routine evaluation and specimen collection per current clinic protocols. This includes a pelvic exam and self-collected or clinician-collected endocervical swabs for female participants; or a genital exam and clinician-collected urethral discharge specimen for male participants per standard clinic collection protocols. For participants randomized to the intervention arm, either one vaginal swab (female participants) or urine sample (male participants) will be collected for testing by the binx platform.

The endocervical and urethral specimens collected for use in this study will be processed immediately for point-of-care gram stain and additional specimen plated for gonorrhea culture as per current clinic protocols; to be sent to the Massachusetts Department of Public Health (DPH). Additional specimens will be sent to the DPH for nucleic acid amplification testing (NAAT) for gonorrhea and chlamydia, as per current clinic protocols. Participants in both the control and intervention arm of the study will have a point-of-care gram stain created, from either vaginal or endocervical swab (for female participants) or urethral swab (for male participants). All point-of-care gram stains will be performed by staff up to date with proficiency testing as per the MGH point of care testing committee. The point-of-care gram stain requires approximately 5-10 minutes for specimen processing/creation of the gram stained slide and reading of the slide. The point-of-care gram stain will be processed and read in the Sexual Health Clinic laboratory space on Cox 5 (room #572). Participants in the control arm will be administered antibiotic therapy in the clinic based on the results of the point-of-care gram stain. Point-of-care gram stain slides for intervention arm participants will be held for later interpretation following the clinical encounter. The gram stain slides from intervention arm participants each week will be labelled with the participant's study number and read at the end of the week. Results will be recorded in the study record.

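### Two ordinal models test the primary outcome, neither is named as primary, and the adjusted model's covariates depend partly on significance in the trial's own data

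*Combined protocol and SAP*

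**What the plan says.** The primary analysis is described only in Section 9, Analysis plan: "Unadjusted and adjusted ordinal logistic regression models will be used to compare the total antibiotics administered". On the adjusted model it says: "Adjusted models will incorporate predictors felt clinically to affect likelihood of antibiotic administration as well as those found to be significant in unadjusted analyses", then "including gender, age, race/ethnicity, and insurance status". No significance threshold for entry is given. The list can be read as four covariates that are always included or as four candidates.

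Section 2, Aim 1, gives the outcome as "comparing the mean number of antibiotic courses administered per patient when evaluated with either point of care gram stain" or the new platform, but names no model. The error rate appears only in the sample size paragraph of Section 9 ("With an alpha of 0.05"), without sidedness and without tying it to either model. Section 3 sets the context: "This study is a pilot randomized controlled trial".

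**The concern.** An alpha of 0.05 means something only if the plan says which test it belongs to. Here one hypothesis is tested by two models, and the second is really a family, because its covariates rest on clinical judgement and on what turns out significant. No section ranks the models or says what follows when one gives p<0.05 and the other does not. Two analysts following the text could fit different adjusted models, or give different models precedence, and report different answers. Because Section 9 states a hypothesis, an alpha and a power, a formal test is intended even though the trial is a pilot.

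**Working it through.** **Inputs from the plan (Section 9).** Alpha 0.05; 100 participants, 50 per arm; control mean 1.13 courses; target 1.017. The target reproduces: 1.13 × 0.90 = 1.017. The stated power is a separate matter and does not bear on this point.

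**Inputs assumed.** The documents give no distribution of courses, no covariate frequencies or effects, no entry threshold and no sidedness. Everything below is therefore a range under stated assumptions.

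**Step 1, bounds.** If the two tests always agreed, the chance of at least one false positive would be 5%. If they were independent it would be 1 − 0.95² = 9.75%. Two models fitted to the same outcomes are strongly correlated, so two correctly sized tests should lie between these.

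**Step 2, simulation.** The model is logit P(Y ≤ k) = θₖ − β·arm − γ′x, with a two-sided Wald test of β.
- Probabilities of 0/1/2 courses: .20/.47/.33 or .10/.67/.23. Both have mean 1.13 (.47 + 2×.33; .67 + 2×.23).
- Covariates: the four named ones, coded with 9 or 5 parameters.
- Prognostic patterns (log odds ratios): none; sex only (1.0); moderate (sex 1.0, race/ethnicity ±0.5, insurance 0.5, age 0.3 per SD); strong (sex 1.5, race/ethnicity ±1.0, insurance 1.0, age 0.6 per SD).
- Screening: a covariate enters if its own likelihood-ratio p<0.05.
- Size: 16 scenarios of 5,000 null trials; Monte Carlo SE 0.3-0.4 points.

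Type I error with one model only: unadjusted 4.5-5.6%; screened 4.6-6.1%; all four covariates 5.2-6.2% (5 parameters) or 5.7-7.0% (9 parameters).

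Type I error if either of two models may count:

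| Prognostic pattern | Unadjusted or screened | Unadjusted or all four |
|---|---|---|
| None | 4.8-5.4% | 5.9-7.2% |
| Sex only | 5.5-6.2% | 6.4-7.4% |
| Moderate | 6.1-6.8% | 6.7-8.6% |
| Strong | 7.6-8.5% | 8.0-9.3% |

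A second simulation used 0/1/2/3 courses with probabilities .15/.60/.22/.03 (mean .60 + .44 + .09 = 1.13) and other codings. It gave 5.5-6.1% and 7.0-7.3% for the two columns.

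**Step 3, separating the Wald excess.** In six null scenarios (.20/.47/.33; none, moderate and strong; both codings; 4,000 trials each), unadjusted-or-all-four gave 6.2-9.0% at nominal p<0.05. With each test first calibrated to exactly 5%, it gave 5.9-7.9%. The unranked choice alone therefore adds 5.9 − 5 = 0.9 to 7.9 − 5 = 2.9 points.

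**Step 4, disagreement.** The arm log odds ratio was set so that the intervention mean is 1.017 (−0.295 to −0.517 across scenarios; 2,000 trials each). The models fell on different sides of p<0.05 in 0.6-11.5% of trials (unadjusted v screened) and 3.6-14.0% (unadjusted v all four). At log odds ratio −0.35, total disagreement was 4.5-13.3%, but one p<0.05 with the other above 0.10 occurred in only 0.5-7.9%.

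**Step 5, candidate remedies.** Arm plus a two-level male/female term gave 4.8-5.7%. To see whether a likelihood-ratio test would remove the four-covariate excess, I ran 12 null scenarios (none, moderate and strong; both codings; both three-level distributions; 4,000 trials each). It gave 5.1-7.0%, against 4.6-6.9% for the Wald test, so it does not. Sparse coding matters more.

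**The case against.** The strongest reply is that the plan says both models will be used, and reporting an unadjusted and an adjusted analysis together is ordinary practice. If both appear, readers see both and nothing is selected out of sight. This stands against a tempting stronger reading, that the plan will report whichever model is more favourable and so loses its 5% error rate. The documents do not say that, so any inflation is conditional. What remains is that no rule says which result decides.

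A reader might also infer that the significance screen itself inflates the error rate. The runs do not support this: the screened model alone gave 4.6-6.1%. The screen matters because it leaves the adjusted model undefined.

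Three further replies hold in part. The figures above 8.6% need the strong pattern, which no section supports, and include Wald excess. Disagreement on p<0.05 includes pairs such as 0.04 and 0.06, so calling all of it opposite conclusions would be too strong. And the four-covariate model with 9 parameters, at 5.7-7.0%, can run no lower than leaving unadjusted and screened unranked in the three weaker patterns (4.8-6.8%). This counts against that choice of covariates, not against naming a primary model.

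Finally, the trial is a pilot, outcomes will also be reported descriptively, and four covariates are named. These points lower the stakes but do not supply a ranking.

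**Conclusion.** The point holds as a gap in specification. Section 9 sets two unranked tests on one hypothesis, with an adjusted model that is not closed, and no other section resolves it. The consequence is small: about 5-8% type I error instead of 5% if either model may supply the headline, with 1-3 points of excess due to the unranked choice, and a split verdict in roughly 1-14% of trials at the planned effect. These sizes rest on assumed outcome and covariate distributions, a two-sided Wald test and a 0.05 entry threshold. That no model is ranked rests on the text alone. A doubled or uncontrolled error rate should not be inferred: the two models are strongly correlated, and the plan states no selective reporting.

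**What to change.** Name one primary model; this is the essential step. Suggested text:

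> The primary analysis is a single ordinal logistic regression of total antibiotics on randomised arm and male/female specimen category, tested two-sided at 0.05. The covariate set is fixed before outcome data are seen. All other models, including the unadjusted model, are sensitivity analyses and do not determine the conclusion. The difference in mean courses between arms is reported with a 95% confidence interval.

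Specimen category is a natural single covariate because Section 6 sets the specimen by it ("either one vaginal swab (female participants) or urine sample (male participants) will be collected for testing by the binx platform") and also the gram-stain cell-count threshold. If the four named covariates are preferred, list them as fixed and keep the coding sparse. A likelihood-ratio test alone will not remove the small-sample excess; a re-randomisation test following the REDCap allocation scheme would address it directly.

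Delete the clause that admits covariates because they are significant in unadjusted analyses. Deleting it without naming a primary model would not be enough. The mean difference belongs alongside because the hypothesis concerns a 10% fall in the mean, which an ordinal odds ratio does not estimate.

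This is a cheap improvement. It needs wording only, with data already planned: "Demographic and clinical data for both cohorts will be obtained from the SHC RedCap database". The cost is losing the freedom to choose covariates after seeing the data. No power loss was seen for the four-covariate model against the unadjusted one at log odds ratio −0.8 (42.4-56.1% v 32.8-55.5%). That is weak reassurance, because the ranges are pooled over scenarios and part of the gain is the liberal test.
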